7.3. Unscheduled Visits

If, during the investigation, a subject requires an unscheduled visit to the clinical site, the following information will be collected, as appropriate:

- Chief complaint prompting the visit. If the reason is an adverse event, the applicable eCRF for the adverse event must be completed and subject record completed as appropriate.
- Date and time of the visit and all procedures completed at the unscheduled visit.
- Review of adverse event and concomitant medications.
- Documentation of any test article dispensed or collected from the subject, if applicable.
- Slit lamp findings (using the Slit Lamp Classification Scale).

If the Investigator withdraws a subject from the study, the final study visit case report forms must be completed indicating the reason(s) why the subject was withdrawn. The subject record must be completed documenting the date and primary reason for withdrawal and the study CRA notified.

Any ocular and non-ocular Adverse Events that are ongoing at the time of the study visit will be followed by the Investigator, within licensure, until they have resolved, returned to pre-treatment status, stabilized, or been satisfactorily explained. If further treatment i.e., beyond licensure is required, the subject will be referred to the appropriate health care provider.

The following information will be collected during an unscheduled visit.

Clinical Study Protocol
Johnson & Johnson Vision Care, Inc.

Unscheduled Visit			
Step	Procedure	Details	
U.1	Reason for unscheduled visit	Indicate if the only reason for the visit is that the subject requires additional test articles. If the reason is other than resupply of previously dispensed lenses, specify the reason for the visit.	
U.2	Chief Complaints (if applicable)	Record the subject's chief complaints for reasons for the unscheduled visit.	
U.3	Adverse Events and Concomitant Medications Review (if applicable)	Review any changes to the subject's medical history or concomitant medications from the previous study visit. Record any changes, and any adverse events.	
U.4	Entrance VA (if applicable)	Record the distance Snellen visual acuity (OD, OS, OU) to the nearest letter, and the type of visual correction being worn (study lenses, habitual lenses, distance spectacles or unaided).	
U.5	Subjective Sphero-cylindrical Refraction (if applicable)	Perform bare-eye subjective sphero-cylindrical refraction with a phoropter (adopt the maximum plus to maximum visual acuity (MPMVA) approach and use the duo-chrome test for binocular balancing) and record the best corrected distance visual acuity to the nearest letter (OD, OS, OU).	
U.6	Slit Lamp Biomicroscopy (if applicable)	FDA Slit Lamp Classification Scale will be used to grade the findings. If the clearance of the fluorescein needs to be expedited, preservative-free rewetting drops may be instilled.	
U.7	Dispensing (if applicable)	If the subject requires additional lenses to complete the wear period and is eligible to do so, provide additional lenses per the dispensing instructions given in the detailed study procedures.	
U.8	Exit Visual Acuity (if applicable)	Record the distance Snellen visual acuity (OD, OS, OU) to the nearest letter, and the type of visual correction being worn (study lenses, habitual lenses, distance spectacles or unaided).	

Note: If the only reason for the unscheduled visit is that the subject requires additional test articles, only the dispensing information needs to be recorded.

Clinical Study Protocol

Johnson & Johnson Vision Care, Inc.

7.4. Laboratory Procedures

Not applicable.

8. SUBJECTS COMPLETION/WITHDRAWAL

8.1. Completion Criteria

Completion criteria will be assessed for each phase separately. Subjects are considered to have completed a study phase if they:

- provided informed consent.
- they are eligible.
- have not withdrawn/discontinued from the study for any reason described in Section 8.2.
- completed all scheduled visits through the final visit (Visit 4).

If all visits were completed but an additional visit is considered necessary for subject care, follow the requirements for unscheduled visits in Section 7.3.

8.2. Withdrawal/Discontinuation from the Study

A subject will be withdrawn from the study for any of the following reasons:

- Subject withdrawal of consent.
- Subject not compliant to protocol
- Subject lost to follow-up.
- Subject no longer meets eligibility criteria (e.g. the subject becomes pregnant).
- Subject develops significant or serious adverse events necessitating discontinuation of study lens wear
- Subjects who have experienced a Corneal Infiltrative Event (CIE).
- Investigator's clinical judgment regarding the subject safety reasons (that it is in the best interest of the subject to stop treatment).
- Subject not compliant with study lens wear schedule
- Subject not successfully dispensed due to lack of efficacy and safety including poor vision, poor comfort or unacceptable fit.

For discontinued subjects, the Investigator will:

- Complete the current visit (scheduled or unscheduled).
- Complete the Final Evaluation, indicating the reason that the subject was discontinued from the study.
- Record the spherocylindrical refraction with best corrected distance visual acuity.
- Collect used test article(s) (worn or brought to the visit) from the subject and discard them, unless otherwise stated in Section 7.2.
- Collect all unused test article(s) from the subject.
- Make arrangements for subject care, if needed, due to their study participation

Additional subjects will not be enrolled if a subject discontinues from the study prematurely.

Clinical Study Protocol

Johnson & Johnson Vision Care, Inc.

In cases where a subject is lost to follow-up, every possible effort must be made to contact the subject and determine the reason for discontinuation/withdrawal. The measures taken to follow up must be documented including two written attempts and a certified letter (or equivalent) as the final attempt.

9. PRE-STUDY AND CONCOMITANT INTERVENTION/MEDICATION

Concomitant medications will be documented during screening and updated during the study.

Disallowed medications for this study include: Table 4

Concomitant therapies that are disallowed include: Table 4

9.1. Systemic Medications

Certain systemic medications are known to have a higher likelihood to interfere with contact lens wear, chiefly by disrupting the tear film. A summary of disallowed medications is shown in Table 4. Subjects with a history of taking these medications will be allowed to enroll only if:

- The medications have been taken on a continual or routine basis for at least 6 months and the subject has demonstrated successful contact lens wear during this time.

Or

- The subject previously used these medications on a temporary basis and has ceased that medication at least 1 week prior to signing the informed consent.

Table 4: Disallowed Systemic Medications

Class of Drug	Common Indication(s)	Common Examples
Anticholinergics	Irritable bowel syndrome, Parkinson's disease, peptic ulcer, cystitis, nasal congestion, cold symptoms, overactive bladder, COPD	Bentyl, Spiriva, Atrovent, Hyosyne, Levsin, Symax Fastab, Symax SL, Homax SL, Cogentin, Transderm Scop, etc.
Oral Phenothiazines	Antipsychotic disorders (schizophrenia, mania)	Compazine, Mellaril, Thorazine, Phenagran, etc.
Oral/Inhaled Corticosteroids	Arthritis, colitis, asthma, bronchitis, allergic or inflammatory conditions	Cortisone, Prednisone, Hydrocortisone, Medrol, Kenalog, Flonase etc.
Oral Retinoids	Seborrhea, acne	Isotretinoin, Acitretin, Alitretinoin, etc.
Oral Tetracycline	Urinary Tract Infection, acne, chlamydia, gonorrhea	Sumycin, Achromycin V, etc.

Clinical Study Protocol

Johnson & Johnson Vision Care, Inc.

10. DEVIATIONS FROM THE PROTOCOL

Investigator will notify study sponsor upon identification of a protocol deviation. Protocol deviations must be reported to the sponsor within 24 hours after discovery of the protocol deviation. The Investigator will report deviations per IRB/IEC requirements. All deviations will be tracked, and corrective actions implemented as appropriate.

If it becomes necessary for the Investigator to implement a deviation in order to eliminate an immediate hazard to the trial subject, the Investigator may implement the deviation immediately without notification to the sponsor. Within 24 hours after the implemented deviation, the Investigator must notify and provide the rationale to the Sponsor and, as required, the IEC/IRB.

If the deviation potentially impacts the safety of patient or changes the technical integrity of the study, then it must be reported to IEC/IRB. This is a "Major Deviation". Deviations that contradict the information contained in the Informed Consent/Accent forms will be considered Major Deviations.

Minor deviations have no substantive effect on patient safety or technical integrity of the study. They are often logistical in nature.

Protocol waivers are prohibited.

Table 5 lists examples of deviations that will constitute major and minor protocol deviations for this study.

Table 5: Examples of Major and Minor Protocol Deviations

Deviation category	Major deviation	Minor deviation
Out-of-window visit	Visit attended more than 2 days out of visit window defined in study procedures	Visit attended 2 or fewer days out of visit window defined in study procedures
Unanswered PRO questions	For questionnaires where data is related to a primary or secondary endpoint, more than 2 PRO questions are unanswered (i.e., left blank).	For questionnaires where data is related to a primary or secondary endpoint, 2 or fewer PRO questions are unanswered (i.e., left blank).
Insufficient wear of study lenses	Subject does not wear study lenses for 3 or more days between fitting and follow-up visits.	Subject does not wear study lenses for 2 days between fitting and follow-up visits.

Clinical Study Protocol

Johnson & Johnson Vision Care, Inc.

In the case of a major protocol deviation, the decision of whether or not the subject will be excluded from the Per-Protocol analysis population will be made at the time of cohort review.

11. STUDY TERMINATION

If more than 2 subjects in the investigational soft contact lens group develop serious expected (e.g., definite or probable MK) or unexpected device related adverse events, the study will be suspended. Upon review and consultation with IRB, DMC, and JJVC Safety Review committee, the study may be terminated. This potential stopping rule is established based on our trial involving approximately 200 subjects wearing the investigational soft contact lens for up to 3 years with an assumed MK rate that is below 0.2% per patient-year. The rate of 0.2% per patient year is the established rate for extended wear lenses in adults, which was requested by the FDA as a criterion for evaluating a contact lens for pediatric use in an FDA response to a pre-IDE submission. To be conservative, 200 independent patient years were used in the calculation. The probability of observing 2 cases or more incidents of MK is 0.061, and 3 cases or more incidents of MK is 0.007 (given an MK rate of 0.2% per patient year).

The occurrence of one or more Unanticipated Serious Adverse Device Effect (USADE), or any SAE where the relationship to study agent cannot be ruled out, may result in stopping further dispensing of test article. In the event of a USADE or SAE, the Sponsor may unmask the treatment regimen for the subject(s) and will discuss this with the Investigator before any further subjects are enrolled.

The Sponsor will determine when a study will be stopped. The Principal Investigator always has the discretion to initiate stopping the study based on patient safety or if information indicates the study's results are compromised.

JJVC reserves the right to terminate the study at any time for any reason. Additionally, the IEC/IRB reserves the right to terminate the study if an unreasonable risk is determined. The study can be terminated by the Principal Investigator at the individual clinical site due to specific clinical observations, if in their opinion, after a discussion with JJVC, it is determined that it would be unwise to continue at the clinical site.

JJVC (and the IEC/IRB and DMC, if applicable) will evaluate all adverse events. If it is determined that an adverse event presents an unreasonable risk, the investigation, or that part of the investigation presenting the risk, will be terminated as soon as possible.

Should the study be terminated (either prematurely or as scheduled), the Investigator will notify the IEC/IRB and Regulatory Authority as required by local regulatory requirements.

Clinical Study Protocol

Johnson & Johnson Vision Care, Inc.

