Microbiology or Other Laboratory Testing	None.
Study Termination	The occurrence of an Unanticipated Adverse Device Effect (UADE) or Serious Adverse Event (SAE) for which a causal relationship to a test article cannot be ruled out, will result in stopping further dispensing investigational product. In the event of a UADE or SAE, the Sponsor Medical Monitor may unmask the treatment regimen of subject(s) and may discuss this with the Principal Investigator before any further subjects are enrolled.
Ancillary Supplies/ Study-Specific Materials	Preservative-free saline and lens vials will be supplied in case needed for lenses associated with any adverse events or product quality complaints.
Principal Investigator(s) and Study Institution(s)/Site(s)	A full list of Principal Investigators, clinical sites, and institutions is kept separately from the Study Protocol and is included in the study Trial Master File.

Clinical Study Protocol

Johnson & Johnson Vision Care, Inc.

Figure 1: Study Flowchart

Clinical Study Protocol

Johnson & Johnson Vision Care, Inc.

COMMONLY USED ABBREVIATIONS, ACRONYMS AND DEFINITIONS OF TERMS

ADE	Adverse Device Effect
ADHD	Attention Deficit Hyperactivity Disorder
AE	Adverse Event/Adverse Experience
BSCVA	Best Spectacle Corrected Visual Acuity
CFR	Code of Federal Regulations
COM	Clinical Operations Manager
COVID-19	Coronavirus Disease 2019
CRA	Clinical Research Associate
CRF	Case Report Form
CRO	Contract Research Organization
████████	████████
D	Diopter
DMC	Data Monitoring Committee
eCRF	Electronic Case Report Form
EDC	Electronic Data Capture
ETDRS	Early Treatment Diabetic Retinopathy Study
FDA	Food and Drug Administration
GCP	Good Clinical Practice
HIPAA	Health Insurance Portability and Accountability Act
HIV	Human Immunodeficiency Virus
IB	Investigator's Brochure
ICH	International Council for Harmonization
IEC	Independent Ethics Committee
IRB	Institutional Review Board
ISO	International Organization for Standardization
ITT	Intent-to-Treat
JJVC	Johnson & Johnson Vision Care, Inc.
LASIK	Laser-Assisted in Situ Keratomileusis
OD	Right Eye
OS	Left Eye
OU	Both Eyes
PIG	Patient Instruction Guide
PQC	Product Quality Complaint
PRK	Photorefractive Keratectomy
PRO	Patient Reported Outcome
QA	Quality Assurance
SAE	Serious Adverse Event/Serious Adverse Experience
SAP	Statistical Analysis Plan
SAS	Statistical Analysis System
SD	Standard Deviation
UADE	Unanticipated Adverse Device Effect
USADE	Unanticipated Serious Adverse Device Effect

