1.2. Intended Use of Investigational Products

ACUVUE® OASYS 1-Day contact lenses are indicated for daily disposable wear for the optical correction of refractive ametropia (myopia and hyperopia) in phakic or aphakic persons with non-diseased eyes who may have 1.00 D or less of astigmatism.

PRECISION1™ spherical soft contact lenses are indicated for the optical correction of refractive ametropia (myopia and hyperopia) in phakic or aphakic persons with non-diseased eyes with up to approximately 1.50 diopters (D) of astigmatism that does not interfere with visual acuity.

In this research study, the test articles will be available in a limited range of minus powers suitable for use by participants with certain levels of myopia. The study population will be limited to persons between the ages of 18 to 40 who may have 1.00 D or less of astigmatism.

The study participants will wear each of the study lens types in random order. Each study lens type will be worn bilaterally in daily wear, daily disposable modality for approximately one week (6 to 8 days).

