4.3. Enrollment Target and Study Duration

During Phase I, approximately 65 subjects will be enrolled to target 60 subjects completing. The number of subjects enrolled in phase II will depend on the interim analysis conducted after phase I. A maximum of 300 subjects can be enrolled into phase II. The study duration including the enrollment period is expected to be approximately 6 weeks for phase I and additional 18 weeks for phase II. Subjects who are discontinued prior to the final evaluation in each phase may be replaced at the discretion of the study sponsor. The investigation will end at the time that the study data is hard locked.

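### Section 11 justifies its suspension rule with 200 patient-years, but this trial gives at most 6 to 8 on O1D; the single-event stop and the DMC step also conflict with other sections

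*Combined protocol and SAP*

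**What the plan says.** Section 11 (Study Termination) has two tiers.

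- **Suspension tier.** The study is suspended if more than 2 subjects in the investigational lens group have serious device-related events. Termination may follow after consultation with the IRB, a DMC and the sponsor's safety review committee. The justification is that the "stopping rule is established based on our trial involving approximately 200 subjects wearing the investigational soft contact lens for up to 3 years", at an assumed MK rate below 0.2% per patient-year. It adds: "To be conservative, 200 independent patient years were used in the calculation". The resulting probabilities are 0.061 for 2 or more MK cases and 0.007 for 3 or more.
- **Single-event tier.** One USADE, or one SAE whose relationship cannot be ruled out, "may result in stopping further dispensing of test article". The sponsor will then discuss unmasking with the investigator before enrolling further subjects.

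Other sections describe the trial and its oversight differently.

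- Section 1.2: "Each study lens type will be worn bilaterally in daily wear, daily disposable modality for approximately one week (6 to 8 days").
- Section 4.3, Phase I: "approximately 65 subjects will be enrolled to target 60 subjects completing". Phase II: "A maximum of 300 subjects can be enrolled into phase II".
- Synopsis, Study Termination row: one UADE, or one SAE whose causal relationship cannot be ruled out, "will result in stopping further dispensing investigational product". The medical monitor "may discuss this with the Principal Investigator before any further subjects are enrolled".
- Section 16.4: a DMC is not applicable.
- Section 4.1: both phases are 2x2 crossovers.

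**The concern.** The rationale describes a different study: about 200 people followed for up to three years, with a rate for extended-wear lenses and a criterion for pediatric use. This trial has about a week of daily disposable wear per lens in adults aged 18 to 40. The two probabilities are presented as properties of the rule, and an IRB or site reading Section 11 would take them as such.

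The wording conflicts matter more if an event occurs. Section 13.1 lists MK as an ocular SAE, so a first MK whose relationship cannot be ruled out reaches the single-event tier well before a third case reaches the suspension tier. At that point the synopsis requires a stop and Section 11 leaves it to discretion. The terms differ too: the synopsis says UADE and Section 11 says USADE, while Section 13.1 defines only UADE.

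**Working it through.** **1. The plan's own figures.** With 200 patient-years at 0.002 per year, Binomial(200, 0.002) gives P(2 or more) = 0.0614 and P(3 or more) = 0.0078. These match the printed 0.061 and 0.007, the second cut rather than rounded. Using 600 patient-years (200 x 3) would give 0.337 and 0.120, so 200 was the input. The calculation is sound for that input.

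**2. Exposure in this trial.** Maximum enrolment is 65 + 300 = 365 (Section 4.3), with 6 to 8 days on O1D (Section 1.2).

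Patient-years = subjects x days / 365.25. For example, 365 x 7 / 365.25 = 6.995.

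**3. MK probabilities at the plan's rate.** Cases are Poisson with mean = patient-years x 0.002. At 7 days the mean is 6.995 x 0.002 = 0.01399.

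| Subjects | Days on O1D | Patient-years | P(1 or more) | P(2 or more) | P(3 or more) |
|---|---|---|---|---|---|
| 365 | 6 | 5.996 | 1.19% | 7.13e-5 | 2.85e-7 |
| 365 | 7 | 6.995 | 1.39% | 9.70e-5 | 4.52e-7 |
| 365 | 8 | 7.995 | 1.59% | 1.26e-4 | 6.73e-7 |
| 65 (Phase I only) | 6 | 1.068 | 0.21% | 2.28e-6 | 1.62e-9 |
| 65 (Phase I only) | 7 | 1.246 | 0.25% | 3.10e-6 | 2.57e-9 |
| 65 (Phase I only) | 8 | 1.424 | 0.28% | 4.05e-6 | 3.84e-9 |

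The ratio of 200 to O1D patient-years at maximum enrolment is 33.4, 28.6 and 25.0 for 6, 7 and 8 days.

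**4. If events on either lens count.** Wear doubles to 12 to 16 days per subject, or about 12.0 to 16.0 patient-years, which is 16.7 to 12.5 times below 200. At 14 days the mean is 0.02798, P(1 or more) is about 2.8% and P(3 or more) about 3.6e-6.

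**5. What 0.007 would require here.** P(3 or more) = 0.007 needs a Poisson mean of 0.382. Over 6 to 8 patient-years that is 0.382/6 = 6.4% down to 0.382/8 = 4.8% per year, or 32 to 24 times the 0.2% reference.

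**6. Wording, side by side.**

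| Item | Synopsis or other section | Section 11 |
|---|---|---|
| Dispensing after one qualifying event | will stop | may stop |
| Discussion with investigator before further enrolment | may (medical monitor) | will (sponsor) |
| Term for the device effect | UADE | USADE |
| DMC | not applicable (16.4) | consulted without qualification at suspension; 'if applicable' in the last paragraph |
| Unit counted | crossover, both lenses assigned to each subject (4.1) | investigational lens group |

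O1D only is the likelier meaning of the last item. Section 1.1 names O1D as Test, and Section 13.1 separates the investigational device from the comparator. It is not stated, and the heading of Section 1.1 calls both lenses investigational products.

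**The case against.** The strongest reply is that little depends on the exposure text. The count of more than 2 can be applied without any probability. The sponsor, investigators and IEC/IRB keep their own powers to stop. The passage can also be read as stating where the rule came from, and a reader who knows that lenses are worn for about a week can see that it describes other circumstances. All of this limits the consequence. It does not make the figures correct for this trial.

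The DMC and group wording can be resolved by reading sections together: with no DMC, that consultation falls away and the other two bodies remain, and the group is probably O1D. This is fair, and both are cleanup items. The difference over discussion with the investigator is also minor, and the two passages name different actors.

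A mandatory stop after one event carries a cost. Section 13.1 lists iritis as an ocular SAE, and Section 13.2.1 defines possibly related as causality that cannot be excluded, so one possibly related iritis could halt dispensing. This stands as a reason to leave the choice of rule to the sponsor. It is no reason to keep two different rules.

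**Conclusion.** The concern holds. At maximum enrolment O1D exposure is 6.0 to 8.0 patient-years, 25 to 33 times below the 200 used. MK-only P(3 or more) is 4.5e-7 at 7 days against the stated 0.007, and P(2 or more) is 9.7e-5 against 0.061. Counting both lenses narrows the gap to about 12 to 17 times and does not change the conclusion.

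These figures assume full Phase II enrolment and complete wear; dropouts, a permitted missed day or a smaller Phase II would lower exposure. They also use 0.2% per patient-year, which the plan treats as an upper bound, so they are upper figures for MK. The rule counts other serious device-related events as well. The documents give no rate for those, so the full trigger probability cannot be computed.

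The will/may conflict is the part most likely to matter. At the plan's rate, the chance of at least one MK on O1D is about 1.4% at maximum enrolment and 0.25% if only Phase I runs. Neither section says which wording governs. Subjects remain protected by the other stopping powers, and no efficacy analysis is affected.

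**What to change.** Amend Section 11 and the synopsis together.

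1. Delete the 200-subject, three-year rationale and the 0.061 and 0.007 figures, or replace them with values for this trial's exposure, labelled MK only.
2. State one single-event rule in both places, using one defined term. The choice is the sponsor's. The more protective option is a mandatory stop of dispensing pending review, with more than 2 subjects as a second tier. If that is chosen, the sponsor should accept that a single possibly related ocular SAE, such as iritis, could pause dispensing.
3. Use the same verb in both places for the discussion with the investigator before further enrolment.
4. Replace the group wording with crossover language that says whether O1D events only, or events on either lens, are counted.
5. Remove the DMC from the suspension step, leaving the IRB and the sponsor's safety review committee.

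The change is a text amendment. Sample size, visits, procedures and analyses stay as they are.
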